### Grade 3:

- If the AE is resolved before the time of the next scheduled infusion, or within ≤10 days after the last infusion, treatment will be continued with a dose reduction of 1 step (Section 6.5.2) after recovery.
- If the AE is resolved in 10 to 14 days after the last infusion, omit 1 dose. After recovery, treatment will resume with dose reduction by 1 step. Treatment will restart with the lead-in dose
- If the AE is not resolved in ≤14 days after the last infusion, treatment will be permanently discontinued.
- If the patient experiences a second episode of the same AE, the study treatment will be permanently discontinued.

#### Grade 4:

- The next infusion will be omitted.
- If the AE resolves in ≤14 days after the last infusion, if there is perceived benefit, and the Investigator and Sponsor agree, treatment will restart with the lead-in dose. Dose reduction by 1 step will be applied.
- If the AE is not resolved in ≤14 days after the last infusion, treatment will be permanently discontinued.
- If the patient experiences a second episode of the same AE, the study treatment will be permanently discontinued.

Guidelines for the resumption of treatment following treatment interruption secondary to AEs other than hematological AEs, CRS, or infusion-related reactions are provided in Table 9.

Table 9 - Dose delay and dose modification for adverse events not including hematological adverse events, cytokine release syndrome, or infusion-related reactions

Grade	Condition	Dur	ation of adverse e	vent	Second	Third
	to Continue Treatment	Resolved in <10 days after last infusion	Resolved in 10 to 14 days after last infusion	Persisting >14 days after last infusion	Episode	Episode
1	Not applicable		No change		No change	No change
2	Recovery to Baseline or Grade ≤1	Administer as planned on recovery with dose as planned.	Omit 1 dose Restart after AE resolved. Treatment will restart with the lead-in dose. May escalate to planned dose level.	Omit 1 dose. Restart after AE resolved. Treatment will restart with the lead-in dose. May escalate to planned dose level.	Allowed. Same recommend- ation as for first episode.	Permanent discontinua- tion a
3	Recovery to Baseline or Grade ≤1	Administer as planned on recovery. Dose reduction by 1 step.	Omit 1 dose. Restart after AE resolved. Dose reduction by 1 step and treatment will restart with the lead-in dose. Do not escalate past target dose.	Permanent discontinuation a	Permanent discontinua- tion a	Not applicable
4	Recovery to Baseline or Grade ≤1	Restart after AE re clinical benefit. Tre with dose reductio the lead-in dose. I	1 dose. solved if evidence of atment restart will be on by 1 step and with Do not escalate past et dose.	Permanent discontinuation a	Permanent discontinua- tion a	Not applicable

a If permanent discontinuation is mandated but there is evidence of clinical benefit and the AE has resolved, study treatment may continue if the Investigator and the Sponsor agree

AE=adverse event

# 6.6 EXPANSION COHORT TO CONFIRM THE MTD

Approximately 37 patients will be treated at the RP2D of SAR440234 to collect safety, pharmacokinetic, pharmacodynamic, and preliminary efficacy data. Patients treated at the RP2D in the Dose Escalation Part (except B-ALL patients) together with the patients treated in the Expansion Part to a total of the first 17 patients treated at the RP2D (Stage 1 Phase 2), will be included in the efficacy analysis.

Additional or unexpected toxicities will also be explored using all the data gathered during the study course (not only at the RP2D). The occurrence of cumulative toxicity, and toxicities meeting the DLT criteria observed after the DLT observation period, if any, will also be assessed. The preliminary antitumoral activity (ie, tumor response) of the drug will be evaluated according to the IWG 2003 recommendations for AML (19) and the revised 2000 criteria for HR-MDS (34), and the 2016 NCCN Guidelines for ALL (Appendix D, Appendix F, and Appendix G).

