### 6.9 INTERIM ANALYSIS

An interim analysis is planned after the first 17 patients of the Expansion Part. Refer to Section 13.5 for details on interim analysis.

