# 13 STATISTICAL CONSIDERATIONS

The content of this section is the Statistical Analysis Plan for the study.

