#### 13.1.2 Expansion part

A Simon's 2-stage design (optimal) will be used. If ≤3 responses (CR, CRi or PR) are observed on the first 17 patients treated, the alternative hypothesis of at least 40% response rate will be rejected. Otherwise, accrual will continue to the full sample size of 37 patients. Overall, this procedure has 90% statistical power (1-sided alpha of 10%) to reject a null response rate of 20% in a 1-sample test for a binomial proportion (East version 6.4, Cytel Software, Cambridge, MA). Eleven (11) responses on 37 patients will be necessary to reject the null hypothesis.

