#### 13.5 INTERIM ANALYSIS

In the Expansion Part, an interim analysis is planned when 17 patients are treated in order to decide, based on preset criteria, if the recruitment of planned additional patients is justified. If 3 or fewer responses (CR, CRi, or PR) are observed on the first 17 patients, the study will be stopped for futility.

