2 SAMPLE SIZE DETERMINATION

It is anticipated that approximately 72 patients (67 to 77 patients) will be enrolled in this study (Dose Escalation and Expansion Parts).

Dose Escalation Part

It is anticipated that approximately 30 to 40 DLT-evaluable patients will be entered in the Dose Escalation Part. The actual sample size will vary depending on DLTs observed and number of dose levels actually explored.

Any patient who is not evaluable for DLT, ie, who discontinues the study treatment before the end of Cycle 1 for any reason other than DLT, or who did not receive treatment as planned, will be replaced.

Expansion Part

It is hypothesized that SAR440234 would induce a response rate of 40% and that the null hypothesis for ORR is 20%. Under these hypotheses and using a Simon 2-stage design (optimal), with a 1-sided 10% significance level and a power of 90%, it is planned to enroll 37 patients in the Expansion Part of the study. Eleven (11) responses out of 37 patients will be necessary to reject the null hypothesis (H_0 response rate = 20%).

An interim analysis of the ORR will be done after treatment of the first 17 patients through 2 cycles. If 3 or fewer responses (CR, CRI, or PR) are observed, the Expansion Part will be stopped due to futility.

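### Protocol 6.6 and 6.9 fill the 17 Stage 1 places from different patients, and no section says whether pooled escalation patients count towards the 37

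*Protocol*

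**What the plan says.** Protocol 6.6 describes Stage 1 as "Patients treated at the RP2D in the Dose Escalation Part (except B-ALL patients) together with the patients treated in the Expansion Part" and continues "to a total of the first 17 patients treated at the RP2D (Stage 1 Phase 2), will be included in the efficacy analysis". It also says "Approximately 37 patients will be treated at the RP2D of SAR440234", without stating which part of the study those patients come from.

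Protocol 6.9 reads "An interim analysis is planned after the first 17 patients of the Expansion Part" and refers to 13.5 for details. Protocol 13.5 reads "In the Expansion Part, an interim analysis is planned when 17 patients are treated".

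Protocol 13.1.2 gives the rule, "If ≤3 responses (CR, CRi or PR) are observed on the first 17 patients treated", and requires 11 responses in 37 to reject the null. It does not say which part the 17 come from. Section 13 introduces itself with "The content of this section is the Statistical Analysis Plan for the study" and never mentions escalation patients in its account of the Expansion Part. SAP 2 has "An interim analysis of the ORR will be done after treatment of the first 17 patients through 2 cycles", again without a source.

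On numbers, the synopsis and Protocol 7.1 plan 37 patients for the Expansion Part, separate from 30 to 40 in the Dose Escalation Part.

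On the denominator, Protocol 13.4.8 names no population for ORR. The default in 13.4 is all treated patients; 13.3.4 and SAP 4.1 use only patients with a post-baseline disease assessment.

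**The concern.** The futility rule of at most 3 responses in 17 is the go/no-go decision for the Expansion Part, and its membership depends on which section is followed. Under 6.6, patients from the escalation cohort at the RP2D occupy some of the 17 places; under 6.9 they occupy none. The Expansion Part opens only after escalation is complete (Protocol 6.1), so the responses of the carried-in patients would largely be known when someone had to choose between the sections. The definition should be fixed beforehand.

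The second gap matters more for error control. If 6.6 governs Stage 1 and the enrolment sections govern accrual, the total analysed can exceed 37 while the bound of 11 stays where it is.

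**Working it through.** **Inputs from the documents.** Null ORR 0.20, alternative 0.40, one-sided alpha 0.10, power 0.90 (synopsis, SAP 2). Stop at 3 or fewer responses in 17; reject with at least 11 in 37 (Protocol 13.1.2).

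**Assumed input.** k is the number of non-B-ALL escalation patients treated at the RP2D. The documents give no value. I use 3 and 6, the cohort sizes of a 3+3 level. Patients with B-ALL would lower k, and Protocol 6.3 foresees levels with more than 6 patients, so 6 is not a ceiling.

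**Step 1: reproduce the plan.** With one set of 37 exchangeable patients,

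P(reject | p) = Σ over x = 4 to 17 of Bin(x; 17, p) × P[Bin(20, p) ≥ 11 − x].

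This gives 0.0948 at p = 0.20 and 0.9033 at p = 0.40. The probability of stopping at Stage 1 is 0.549 and 0.046 respectively. A search for the optimal design under these constraints returns the same 3/17 and 11/37, so the stated design is right. It holds equally for a pooled set if the total is 37 and escalation and Expansion patients share one response rate.

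**Step 2: pooled Stage 1, 37 Expansion patients still enrolled, all counted, bound 11.** Stage 1 uses k escalation and 17 − k Expansion patients. Stage 2 then has 37 − (17 − k) = 20 + k patients, and the total is 37 + k. Replace 20 by 20 + k in the formula (23 or 26).

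**Step 3: pooled Stage 1, final test on the 37 Expansion patients only.** Let a be responses among the k escalation patients and s responses among the first 17 − k Expansion patients. Continue if a + s ≥ 4; reject if s + Bin(20 + k, p) ≥ 11:

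P(reject | p) = Σ over a + s ≥ 4 of Bin(a; k, p) × Bin(s; 17 − k, p) × P[Bin(20 + k, p) ≥ 11 − s].

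| Reading | alpha, k = 3 | alpha, k = 6 | power, k = 3 | power, k = 6 |
|---|---|---|---|---|
| One set, total 37 | 0.0948 | 0.0948 | 0.9033 | 0.9033 |
| Pooled interim, 37 + k counted | 0.138 | 0.184 | 0.932 | 0.945 |
| Pooled interim, final on 37 Expansion patients | 0.088 | 0.080 | 0.898 | 0.894 |

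Only the second reading breaks the 10% limit. The third costs a little power.

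**Step 4: the ORR denominator.** With an assumed 2 of 37 patients unassessed, 10 responses are 10/37 = 27.0% of treated patients (Clopper-Pearson 95% interval 13.8 to 44.1%) or 10/35 = 28.6% of assessed patients (14.6 to 46.3%). Ten responses miss the bound of 11 either way.

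**The case against.** The strongest objection is that nothing now depends on this. SAP 4.3, 4.4, 4.6 and 4.9 drop the efficacy endpoints, formal testing and the interim analysis. That stands, and limits the point to the design as written.

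Next, the conflict is narrow. Only 6.9 expressly takes the 17 from the Expansion Part. Section 13.5 can be read as naming the study phase, and 7.1 gives enrolment counts rather than an analysis set. This also stands. But 6.6 labels its 17 as Stage 1 of Phase 2, which ties it to the same look as 6.9, and the two sentences cannot both be followed if any eligible escalation patient was treated at the RP2D.

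Third, no section states the reading that inflates alpha. True: it arises by combining 6.6 with the enrolment figures. The planned total of 67 to 77 equals 30 + 37 to 40 + 37, so the 37 were budgeted on top of the escalation patients. Nothing in 6.6 rules the combination out.

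A reader might infer that pooling in itself damages the design. It does not if the total stays at 37 and the patients are exchangeable. A reader might also take the chance that the two candidate sets of 17 give opposite futility decisions (17.4% for k = 3 and 26.4% for k = 6 at a true ORR of 20%) as an error rate. It is sampling variation between overlapping sets, only one of which would be used.

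**Conclusion.** The point holds as a conflict over who makes up Stage 1, with an unresolved question about the 37. It is not a sample-size error: 3/17 and 11/37 deliver alpha 0.0948 and power 0.9033 on a single exchangeable set of 37. The material risk is the reading in which 37 + k patients are tested against an unchanged bound of 11, where alpha is 0.138 or 0.184 for an assumed k of 3 or 6. If only the interim is pooled, alpha stays below 10% and power falls to 0.898 or 0.894.

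The denominator gap is secondary. A reader might infer that an assessed-only population alters the go/no-go decision, but the rule counts responses and an unassessed patient adds none. Only the reported percentage and its interval move.

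Confidence is high for the conflict between 6.6 and 6.9. The sizes depend on k, which the documents neither give nor cap.

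**What to change.** Define one set for both looks, in the same words, in Protocol 6.6, 6.9, 13.1.2 and 13.5. The better choice is Expansion Part patients only, as 6.9 already says, with non-B-ALL escalation patients at the RP2D summarised separately as supportive. If pooling is intended, say so in all four sections and state that the total is 37 including the pooled patients.

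As a minor addition, name the ORR population in 13.4.8. If any ORR is reported beside the rule, also show it over all treated patients in the set.

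The cost is wording; both bounds, alpha and power are unchanged. With Expansion patients only, the futility look waits for 17 new patients instead of 17 − k, which is 14 or 11 for the assumed k of 3 or 6.

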
Table 11 - Evaluation and management of cytokine release syndrome

Grade	Evaluation	Treatment
1	
 
Monitoring at least every 30 minutes:
 
BP, HR, temperature, respiratory rate, oxygen saturation.
 
Symptom assessment.
 
	Symptomatic treatment with acetaminophen and/or antihistamine, if needed
2	As for Grade 1, with addition of the following: Continuous monitoring of: BP. Oxygen saturation. HR. Monitoring at least every 8 hours, or more frequently if needed, of: PaO 2 . ECG. Blood chemistry.	As for Grade 1, with addition of the following:  • Mandatory transfer of the patient to ICU.  • IV fluid resuscitation and institution of vasopressors.  • Supplemental oxygen.  • Start tocilizumab:  - 8 mg/kg IV once for patients weighing ≥30 kg,  - 12 mg/kg IV once for patients weighing <30 kg,  - If insufficient improvement in CRS within 12 hours, repeat tocilizumab at the same dose every 12 hours for a total of 3 doses.
3	As for Grade 2, with the addition of echocardiography if there is concern for cardiac dysfunction.	
 
As for Grade 2, with addition of the following:
 
High-dose or multiple vasopressors Table 12 to treat hypotension or poor perfusion.
 
If no improvement in CRS within 24 hours, start dexamethasone 10 mg IV every 6 hours.
 

4	As for Grade 3.	As for Grade 3, with the addition of mechanical ventilation if required.

BP=blood pressure, CRS=cytokine release syndrome, ECG=electrocardiogram, HR=heart rate, ICU=intensive care unit, IV=intravenous, PaO2=partial pressure of oxygen in arterial blood

NOTE: Grading of CRS is based according to 2014 National Cancer Institute Consensus Guidelines (see Table 10).

For each patient treated, the hospital must have an available bed in the intensive care unit (ICU) in case the patient develops hemodynamic or respiratory compromise. The ICU should be staffed by a critical care physician who has experience in treating CRS. In addition, the ICU must have the necessary equipment to commence immediate treatment and monitoring of a patient with CRS Grade  $\geq$ 2 before he/she is admitted to ICU. Vital signs monitoring shall be made continuously if CRS Grade  $\geq$ 2 develops.

High dose vasopressors are described in Table 12.

Table 12 - High dose vasopressors

Vasopressor	Dose
Norepinephrine monotherapy	≥20 mg/min
Dopamine monotherapy	≥10 mg/kg/min
Phenylephrine monotherapy	≥200 mg/min
Epinephrine monotherapy	≥10 mg/min
If on vasopressin	Vasopressin + norepinephrine equivalent of ≥10 mg/min
If on combination vasopressors	Norepinephrine equivalent to ≥20 mg/min
(not vasopressin)	

All doses are required for  $\geq$ 3 hours

Property of the Sanofi Group - strictly confidential

Page 67

29-Aug-2019 Version number: 2

Dexamethasone, vasopressors, and oxygen must be tapered quickly after resolution of CRS.

Dexamethasone 20 mg IV must be repeated 5 hours after the start of infusion if CRS Grade 2 has occurred in a previous patient or previous administration in the same patient. This rule will be applied for the same patient who experienced a CRS event for subsequent infusions and for all patients subsequently enrolled at that dose level or higher.

Symptomatic treatment and/or pre-medication may include: diphenhydramine 25 to 50 mg IV (or equivalent), ranitidine 50 mg IV (or equivalent), and acetaminophen 650 to 1000 mg PO 15 to 30 minutes (but no longer than 60 minutes) prior to infusion, or during infusion at the Investigator's discretion.

For patients with CRS Grade ≥2, tocilizumab will be administered at 8 mg/kg infused over 1 hour for patients weighing ≥30 kg (maximum dose 800 mg) or 12 mg/kg infused over 1 hour for patients weighing <30 kg. Another 8 mg/kg or 12 mg/kg dose IV may be administered in patients weighing ≥30 kg (maximum dose 800 mg) or 12 mg/kg for patients weighing <30 kg, respectively, if there is insufficient clinical improvement 12 to 24 hours after the first dose. Up to 3 doses of tocilizumab may be given.

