In this FIH trial, plasma levels of cytokines, including IL-6 and IFN-γ, will be collected, as well as assays for serum CRP and ferritin. Sampling will be performed following the initial dose and after each dose increase, in order to assess for signs of CRS. C-reactive protein is an acute phase reactant produced by the liver, largely in response to IL-6. Serum CRP levels may serve as a surrogate for increases in IL-6 bioactivity (30). During CRS, serum CRP levels may increase by several logs. The serum CRP assay is rapid, inexpensive, and readily available in most hospitals.

In some series, peak CRP levels and fold-change in CRP have identified patients at risk for severe CRS (26). It is important to emphasize, however, that CRP levels are also elevated during infection and cannot be used to distinguish between inflammation caused by infection and inflammation related to CRS. Extreme elevations in serum ferritin have been observed in many patients with CRS after chimeric antigen receptor T-cell infusion, which supports a resemblance between CRS and macrophage activation syndrome/hemophagocytic lymphohistiocytosis.

To assess and record the severity of CRS in individual patients, the National Cancer Institute (NCI) Consensus Guidelines 2014 will be used (29, 31), and the mitigation strategy for CRS (Appendix H), is based on these guidelines. This grading system defines mild, moderate, severe, and life-threatening CRS, regardless of the inciting agent, and provides treatment recommendations with corticosteroids and/or tocilizumab (29). Tocilizumab is a humanized, immunoglobulin (Ig)G1k antihuman IL-6R mAb approved for treatment of rheumatoid arthritis, juvenile idiopathic arthritis, and polyarticular juvenile rheumatoid arthritis (32, 33). Emerging clinical experience at several institutions has demonstrated that tocilizumab is an effective treatment for severe or life-threatening CRS (28). The FDA has approved tocilizumab for the treatment of chimeric antigen receptor T-cell induced severe or life-threatening CRS. The recommended dose of tocilizumab for treatment of CRS is 12 mg/kg IV for patients weighing <30 kg and 8 mg/kg IV for patients weighing ≥30 kg. Doses of tocilizumab should not exceed 800 mg per infusion. It is also recommended that tocilizumab should not be started in patients with an absolute neutrophil count (ANC) <2000/microliter, platelet count <100 000/microliter, or with an ALT or AST >1.5 times the upper limit of normal (ULN).

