# 8.2 NONINVESTIGATIONAL MEDICINAL PRODUCT(S)

**Dexamethasone:** 4 mg/mL for IV injection.

**Tocilizumab:** 200 mg/10 mL vial for IV injection.

**Montelukast:** 10 mg tablet for oral administration.

Dexamethasone 20 mg IV will be instituted as systematic premedication 4 hours and 1 hour prior to each initial IMP administration.

Montelukast tablets 10 mg will be given orally once, 4 hours before the start of SAR440234 infusion.

Dexamethasone 20 mg IV must be repeated 5 hours after the start of infusion if CRS Grade 2 has occurred in a previous patient or previous administration in the same patient. This rule will be applied for the same patient who experiences a CRS event for subsequent infusions and for all patients subsequently enrolled at that dose level or higher.

29-Aug-2019 Version number: 2

For each patient treated, the clinical site must have at least 2 full doses of tocilizumab in the clinical pharmacy ready for immediate administration in case of CRS Grade 2 or above. Guidelines for management of patients with CRS are included in Section 6.7.

For patients with Grade 2 CRS, tocilizumab will be administered at 8 mg/kg infused over 1 hour for patients weighing ≥30 kg (maximum dose 800 mg) or 12 mg/kg infused over 1 hour for patients weighing <30 kg.

If there is insufficient improvement in CRS within 12 hours, tocilizumab may be repeated at the same dose every 12 hours for a total of 3 doses. The interval between consecutive doses should be at least 8 hours. Subcutaneous infusion of tocilizumab is not approved for CRS treatment. Tocilizumab must not be used for prophylaxis of CRS. Patients with Grade 3 or Grade 4 CRS should be treated with tocilizumab as for patients with Grade 2 CRS. For patients with Grade 3 or Grade 4 CRS who do not respond to tocilizumab within 24 hours, dexamethasone 10 mg IV should be given every 6 hours.

For patients weighing ≥30 kg or more, tocilizumab should be diluted in 100 mL of 0.9% or 0.45% sodium chloride injection USP for IV infusion and administered by drip infusion over 1 hour. For patients weighing <30 kg, tocilizumab should be diluted in 50 mL of 0.9% or 0.45% sodium chloride USP for IV infusion and administered by drip infusion over 1 hour. Tocilizumab should not be given as a bolus or push.

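### Table 11, the table that sites are sent to for CRS management, omits the 800 mg tocilizumab maximum stated elsewhere in the protocol, and the repeat-dose rule is worded in conflicting ways

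*Protocol*

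**What the plan says.** The protocol describes tocilizumab treatment of CRS, or the stock held for it, in six places.

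- **Section 6.7.1, Table 11.** The text before the table says that CRS is to be managed as the table describes. From Grade 2 upward the table gives "8 mg/kg IV once for patients weighing ≥30 kg" and states no maximum. Its repeat rule is "If insufficient improvement in CRS within 12 hours, repeat tocilizumab at the same dose every 12 hours for a total of 3 doses".
- **Section 6.7.1, text after Table 12.** Here "tocilizumab will be administered at 8 mg/kg infused over 1 hour for patients weighing ≥30 kg (maximum dose 800 mg". A further dose may be given "if there is insufficient clinical improvement 12 to 24 hours after the first dose", with up to 3 doses in all.
- **Section 8.2.** The same 800 mg maximum is given. After insufficient improvement within 12 hours, "tocilizumab may be repeated at the same dose every 12 hours for a total of 3 doses". This section alone adds a minimum interval of 8 hours between doses. On stock, "the clinical site must have at least 2 full doses of tocilizumab in the clinical pharmacy".
- **Clinical Trial Summary, noninvestigational products.** This gives the same maximum, repeat rule and stock sentence as Section 8.2, without the 8-hour minimum.
- **Section 4.5.4.** "Doses of tocilizumab should not exceed 800 mg per infusion".
- **Section 4.6.** Two doses will be on site for each patient under treatment, with no wording to mark this as a minimum.

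**The concern.** Table 11 is the page that staff would open during a CRS event. It carries no maximum and no pointer to the sentence that does. For a heavy patient, the table read alone gives a larger dose than the protocol allows in four other places.

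Such patients can enter the trial. Section 7.3 sets no upper weight limit, and Section 6.2.1 foresees patients above 140 kg by capping the weight used for SAR440234 dosing. That cap is written for SAR440234 and does not limit tocilizumab.

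The second issue is timing within one section. Under Table 11 the repeat follows a 12-hour check and is worded as an instruction. A page later it is optional and may come at any time between 12 and 24 hours. Section 8.2 and the Summary move to dexamethasone when Grade 3 or 4 CRS has not responded to tocilizumab within 24 hours. By that time one wording can have produced two doses with a third due, and the other only one.

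Severe CRS is the anticipated risk named in Section 4.6, so its rescue instructions should not depend on which page is open.

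**Working it through.** No sample size, power or error rate is involved. The check is a comparison of the passages and simple arithmetic.

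**1. Where the missing maximum matters**

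Inputs: 8 mg/kg for patients of 30 kg or more (Table 11 and all other places), 12 mg/kg below 30 kg, and a maximum of 800 mg (Summary, 4.5.4, 6.7.1 text, 8.2).

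The two readings separate at 800 / 8 = 100 kg.

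| Weight | Table 11 as written | With the 800 mg maximum | Difference per dose |
|---|---|---|---|
| 70 kg | 560 mg | 560 mg | 0 |
| 100 kg | 800 mg | 800 mg | 0 |
| 110 kg | 880 mg | 800 mg | 80 mg (+10%) |
| 120 kg | 960 mg | 800 mg | 160 mg (+20%) |
| 140 kg | 1120 mg | 800 mg | 320 mg (+40%) |

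Below 30 kg the dose stays under 12 × 30 = 360 mg, so the maximum never applies there.

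**2. Repeat rule, side by side**

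| Place | Trigger | Spacing | Force | Maximum doses |
|---|---|---|---|---|
| Table 11 | insufficient improvement within 12 h | every 12 h | directive | 3 |
| Summary | within 12 h | every 12 h | permissive | 3 |
| 8.2 | within 12 h | every 12 h, at least 8 h apart | permissive | 3 |
| 6.7.1 text after Table 12 | 12 to 24 h after first dose | not stated for the third dose | permissive | 3 |

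Twelve-hourly dosing puts the doses at 0, 12 and 24 h. The text after Table 12 lets the second dose fall anywhere from 12 to 24 h. A repeat at exactly 12 h satisfies every version. The 8-hour minimum is compatible with 12-hourly dosing. What conflicts is how long a site may wait, and whether the repeat is an instruction or an option.

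**3. Stock against the stated maximum course**

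The term full dose is not defined, so two readings are shown.

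- If it means the patient's own dose, the minimum of 2 covers 2 of a possible 3. On the 12-hourly schedule the third falls 24 h after the first.
- If it means 800 mg (an assumption), 2 × 800 = 1600 mg. Three doses need 3 × 8 = 24 mg/kg, so 1600 / 24 = 66.7 kg. The minimum covers three doses up to that weight and falls short above it.

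Under either reading, the minimum alone does not guarantee three doses for every eligible weight.

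**The case against.** The strongest reply is that Table 11 is silent and does not state a rival maximum. Later text in the same section gives the 800 mg limit, as do three other places, so a site giving 960 mg would breach four statements. That is correct. A reader might infer that a fully compliant site may choose either dose, and the documents do not support that. What stands is that the designated table, read as printed, yields a dose above the protocol's own maximum and does not point to it.

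The timing difference can fairly be called small, because 12 hours lies inside the 12-to-24-hour window. The longer permitted wait and the difference between instruction and option remain.

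Three stronger readings are tempting and should not be drawn:

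- **That sites cannot supply three doses.** Section 8.2 and the Summary require at least 2 doses ready for immediate use. That is a floor for readiness. Every place except Table 11 makes further doses optional, and nothing excludes resupply within 24 hours. Section 4.6 is flatter in wording but sets no upper limit.
- **That patients of 30 kg or more are offered 8 or 12 mg/kg.** The repeat-dose sentence after Table 12 is clumsy, but it pairs the doses with the weight groups respectively. Every other statement assigns 8 mg/kg to 30 kg and above and 12 mg/kg below.
- **That the inconsistency alters dose-limiting toxicity (DLT) counts.** Some DLT and discontinuation rules use CRS duration (48 and 72 hours), but nothing in the documents links the 800 mg limit or the repeat interval to duration. Grade 3 or 4 CRS is a DLT however long it lasts.

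**Conclusion.** The point holds as an internal inconsistency in rescue-treatment text, with a bounded size.

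- The missing maximum affects only patients above 100 kg. The excess per dose is 80 mg at 110 kg, 160 mg at 120 kg and 320 mg at 140 kg. The documents give no weight distribution, so the share of patients affected is unknown.
- The repeat rule conflicts within Section 6.7.1, and between its later text and Section 8.2 and the Summary: 12 hours against 12 to 24 hours, and directive against permissive.
- The stock statement is the lesser part. The stated minimum does not by itself guarantee the stated maximum course, and no more than that can be said.

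The dose per kilogram, the weight groups and the maximum of 3 doses agree wherever they are stated, so it would be too broad to say that the whole rescue course depends on the page followed. The conclusion rests on reading Table 11 as printed and on the reference to it in Section 6.7.1. No sample size, decision threshold or planned analysis changes. The reason to correct it is patient safety during a CRS event.

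**What to change.** Reconcile the Clinical Trial Summary, Section 4.5.4, Section 4.6, Table 11, the Section 6.7.1 text after Table 12, and Section 8.2. The maximum per infusion, the repeat rule (trigger, spacing, and whether it is an instruction or an option) and the stock statement should read the same everywhere, including in Table 11 itself. It would help to define what a full dose means in the stock sentence and to tidy the repeat-dose sentence after Table 12.

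Which maximum, interval and stock level to state is a clinical decision for the sponsor, and none is proposed here. The cost is protocol wording in six places through an amendment. No change to the design, sample size or SAP follows from it.
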